Cohorts 1 and 2 will initially enroll a total of approximately 19 response-evaluable patients per cohort. If \geq 4 responses (PR or CR) are observed in a cohort, that cohort will be further expanded to a total of approximately 55 response-evaluable patients.

Cohort 3 will initially enroll a total of approximately 9 response-evaluable patients. If ≥ 3 patients experience clinical benefit (CR, or SD ≥ 24 weeks) are observed, the cohort will be further expanded to a total of approximately 24 response-evaluable patients.

Because the combination of TAS-120 and fulvestrant has not been assessed in patients, **Cohort 4** will begin with a safety lead-in period. During the safety lead-in, 3 patients will initially be enrolled and will receive TAS-120 (20 mg QD) and fulvestrant (500 mg) according to the study schedule, with safety follow-up of at least 1 cycle. Patients will be assessed for DLTs and the recommended dose of TAS-120 for this cohort will be determined as follows.

- Of the initial 3 patients, if 0/3 or 1/3 patients present with a DLT, another 3 patients will be enrolled.
 - o If 0/6 or 1/6 patients present with a DLT, the safety lead-in phase will conclude and enrollment will continue to a total of 28 patients treated with TAS-120 (20 mg QD) plus fulvestrant.
- If ≥2/3 or ≥2/6 patients present with a DLT, TAS-120 20 mg QD plus fulvestrant will be defined as a non-tolerated dose level for the combination. Subsequent patients will be treated at a dose of TAS-120 of 16 mg QD plus fulvestrant, and the sequence will be repeated. Initially, 3 patients will be enrolled:
 - o If 0/3 or 1/3 patients present with a DLT, another 3 patients will be enrolled.
 - If 0/6 or 1/6 patients present with a DLT, the safety lead-in phase will conclude and enrollment will continue to a total of 28 patients treated with TAS-120 (16 mg QD) plus fulvestrant.
 - If ≥2/3 or ≥2/6 patients present with a DLT at the dose of TAS-120 at 16 mg QD plus fulvestrant, the assessment of the combination and further enrollment to Cohort 4 will be discontinued.

[figure not shown]

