10.1. Estimation of Sample Size

Up to 168 patients in total may be enrolled in the study.

Please note: the patient numbers given for efficacy analysis are for the response-evaluable population, defined as the subset of treated patients who have measurable disease (or evaluable disease in Cohort 3), who have at least 1 post-baseline disease/tumor assessment, and who have centrally confirmed *FGFR* amplification (Table 13). If a treated patient is not eligible for the response-evaluable population (for example, because *FGFR* amplification cannot be centrally confirmed or no post-baseline tumor assessment is available), additional patients will be enrolled to ensure the correct number of response-evaluable patients for analysis as described below.

Sample size considerations for **Cohorts 1 and 2** (primary endpoint ORR) are based on a 2-stage Optimal Simon design, comparing a poor response of \leq 15% versus a promising response of \geq 30%, at an approximate 5% 1-sided significance level and 80% power.

- In Stage 1 (futility assessment), enrollment will include 19 patients in each cohort and accrual will continue to Stage 2, if at least 4 (21%) of 19 patients respond (CR or PR).
- In Stage 2, if the Stage 1 futility boundary is exceeded, an additional 36 patients will be enrolled, for a total of at least 55 patients per cohort. In Cohorts 1 or 2, with a total of 55 patients, if the observed ORR is 30.9%, the 95% exact confidence interval (CI) is (19.1%, 44.8%).

Sample size considerations for **Cohort 3** (primary endpoint CBR) are also based on a 2-stage Optimal Simon design. The null hypothesis that the true CBR is 25% will be tested against a 1-sided alternative, which yields a type I error rate of 5% and power of 80% when the true CBR rate is 50%. In the first stage, 9 patients will be treated. If there are \leq 2 patients with clinical benefit (ie, CR or SD \geq 24 weeks) in these 9 patients, the cohort will be discontinued. Otherwise, 15 additional patients will be treated for a total of 24 patients. The null hypothesis will be rejected if \geq 11 patients with clinical benefit are observed in 24 patients.

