Sample size considerations for **Cohort 4** (primary endpoint 6-month PFS) are based on a proof-of-concept Phase 2 design, differentiating a null 6-month 25% PFS rate with a target rate of 50%. Approximately 28 patients will be treated. It has approximately 80% power to reject the null hypothesis that the true 6-month PFS rate is \leq 25%, considering a 1-sided alpha (type 1 error rate) of 5%. In addition, 6-12 patients will be enrolled as a safety lead-in. The patients in the safety lead-in who are treated at the recommended Phase 2 dose will be included in the main cohort of 28 patients. Thus up to 34 patients may be enrolled for this cohort.

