6.4. Efficacy Analyses

Unless otherwise specified, all efficacy analyses will be performed based on patients in All Treated Population with centrally confirmed FGFR amplification. For Cohort 4 only, patients treated with recommended dose of TAS-120 in All Treated Population with centrally confirmed FGFR amplification will be used for efficacy analyses.

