The exact 2-sided 95% CI based on Clopper-Pearson methodology will be derived for ORR. The null hypothesis will be rejected if at least 15 responders observed out of 55 patients. If 17 responders observed out of 55 patients, the ORR is 30.9% and the 95% exact CI is (19.1%, 44.8%).

CBR (Cohort 3) will be calculated based on the best overall response. Because patients in Cohort 3 have non-measurable disease at baseline, the overall response will be derived based on non-target lesion response and/or the emergence of new lesion(s). The exact 2-sided 95% CI based on Clopper-Pearson methodology will be derived for CBR. The null hypothesis will be rejected if at least 10 patients with clinical benefit are observed out of 24 patients in Cohort 3.

The exact 2-sided 95% CI based on Clopper-Pearson methodology will be derived for 6-month PFS rate (Cohort 4). The null hypothesis will be rejected if at least 14 patients observed to remain alive and progression free at 6 months after the start of treatment out of 28 patients who are treated at recommended dose in Cohort 4.

Table 4. Overall Response Assessment with Target/Non-target Lesion and New Lesions

Target Lesions	Non-target Lesions	New Lesions	Overall Response
CR	CR	No	CR
CR	Non-CR/Non-PD or Not all evaluated	No	PR
PR	Non-PD or Not all evaluated	No	PR
SD	Non-PD or Not all evaluated	No	SD
Not all evaluated	Non-PD	No	Not evaluable
PD	Any	Yes or No	PD
Any	PD	Yes or No	PD
Any	Any	Yes	PD

Table 5. Confirmation Rules for Overall Response of PR and CR

Earlier Response	Later Response	Confirmed Response
(to be confirmed)	(confirmation)	
CR	CR	CR
CR	Not CR or missing	SD
PR	CR or PR	PR
PR	SD or PD or missing	SD
PR	SD and then PR (only one SD in between)	PR
SD	n/a – no confirmation needed	SD
PD	n/a – no confirmation needed	PD

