6.4.1.1. Sensitivity Analyses

The primary efficacy endpoints, ORR (Cohorts 1 and 2), CBR (Cohort 3) and 6-month PFS (Cohort 4), will be analyzed based on the Response Evaluable Set using the same method as that used in the primary efficacy analysis.

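### Cohort 4's fixed cut-off of 14 out of 28 has 57.5% power, not about 80%, even with all 28 analysed, and the plan defines the 28 in three ways without saying how the cut-off follows the number analysed

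*SAP*

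**What the plan says.** **Design assumptions.** Protocol 10.1 sizes Cohort 4 by "differentiating a null 6-month 25% PFS rate with a target rate of 50" percent, "considering a 1-sided alpha (type 1 error rate) of 5" percent. It says of the planned 28 patients: "It has approximately 80% power to reject the null hypothesis". SAP 4.3 repeats this.

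**Decision rule.** SAP 6.4.1 rejects the null hypothesis at 14 or more patients alive and progression-free at 6 months, "out of 28 patients who are treated at recommended dose in Cohort 4". It gives no rule for any other number of patients.

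**Who the 28 are.**
- Treated: in Protocol 3.1, if 20 mg passes the lead-in, "enrollment will continue to a total of 28 patients treated with TAS-120 (20 mg QD) plus fulvestrant". The parallel sentence for 16 mg also counts treated patients, as does the Cohort 4 paragraph of Protocol 10.1. For Cohorts 1 to 3, Section 3.1 counts response-evaluable patients.
- Response-evaluable: the preamble of Protocol 10.1 says "the patient numbers given for efficacy analysis are for the response-evaluable population". It adds that treated patients who fall outside that population, for instance for lack of central confirmation, are made up by further enrolment. SAP 4.3 says the same.
- Confirmed, at the recommended dose: SAP 6.4 states for Cohort 4 that "patients treated with recommended dose of TAS-120 in All Treated Population with centrally confirmed FGFR amplification will be used for efficacy analyses".

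**Timing of confirmation.** Local testing can establish eligibility (Protocol 6.1.1.1). Tissue goes to the central laboratory after enrolment (Schedule of Events), and confirmation is retrospective (Protocol 9.1.3).

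**Ceilings.** Cohort 4 may enrol up to 34 patients and the study up to about 168.

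**Sensitivity analysis.** SAP 6.4.1.1 says the primary endpoints "will be analyzed based on the Response Evaluable Set using the same method as that used in the primary efficacy analysis". SAP 5.3 defines that set without a dose restriction.

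**The concern.** A count of 14 out of 28 is exactly the 50% target rate. A rule that requires the observed rate to reach the target succeeds only a little more than half the time when the target is true, so it cannot deliver 80% power.

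Separately, a fixed count is valid only for the number it was derived for. The plan allows the number analysed to differ from 28 and does not say what the cut-off then becomes. The same data could therefore pass or fail according to which section is followed. At stake is a proof-of-concept decision: a combination that truly reaches 50% could be declared a failure because of the rule rather than the data.

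**Working it through.** **Inputs.** p0 = 0.25, p1 = 0.50, one-sided alpha 0.05, N = 28 (Protocol 10.1); cut-off 14 (SAP 6.4.1). Assumed: confirmation rate c from 0.95 to 0.80, independent of outcome.

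**Formulas.** For cut-off k and N patients, alpha = P(X ≥ k) with X ~ Bin(N, 0.25), and power = P(X ≥ k) with X ~ Bin(N, 0.50).

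**Step 1: the plan's own figure.** At N = 28:

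| Cut-off | Alpha | Power |
|---|---|---|
| 11 | 6.8% | 90.8% |
| 12 | 2.9% | 82.8% |
| 13 | 1.1% | 71.4% |
| 14 | 0.38% | 57.5% |

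The smallest cut-off within 5% is 12, with 82.8% power. So 28 patients do support the approximately 80% claim, but with 12, not 14. A one-sided 2.5% level would give 13, so that does not explain 14 either. The SAP cut-off loses 82.8 − 57.5 = 25.3 points with every patient in the denominator.

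**Step 2: accrual stops at 28 treated, only confirmed patients count, none replaced.** The number of confirmed successes is Bin(28, 0.50c), so power = P(Bin(28, 0.50c) ≥ k):

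| Confirmation c | Cut-off 12 | Cut-off 14 |
|---|---|---|
| 100% | 82.8% | 57.5% |
| 95% | 75% | 47% |
| 90% | 66% | 36% |
| 85% | 56% | 27% |
| 80% | 45% | 19% |

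The cut-off 12 column isolates the denominator effect. The cut-off 14 column combines both problems.

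**Step 3: replacement followed.** The SAP 6.4 set does not require a post-baseline scan, so with 28 response-evaluable patients at the recommended dose it holds at least 28 and possibly more. A fixed 12 would then exceed the stated alpha: 5.07% at N = 30 and 11.9% at N = 34. A fixed 14 stays within alpha (2.8% at N = 34, power 88.5%), but its power moves from 57.5% to 88.5% with a number the plan does not fix.

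**Step 4: ceilings.** 34 = 28 + 6 patients at a dose that failed the lead-in, and 55 + 55 + 24 + 34 = 168. Neither total includes an allowance for replacements. Spare places in Cohort 4 arise only if the second lead-in group is not needed.

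**Step 5: cut-off matched to N** (smallest k with alpha ≤ 5%):

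| N | Cut-off | Power at 50% |
|---|---|---|
| 20 | 9 | 74.8% |
| 21 | 10 | 66.8% |
| 22 | 10 | 73.8% |
| 23 | 10 | 79.8% |
| 24 | 11 | 72.9% |
| 25 | 11 | 78.8% |
| 26 | 11 | 83.7% |
| 27 | 12 | 77.9% |
| 28 | 12 | 82.8% |
| 29 | 12 | 86.8% |
| 30 | 13 | 81.9% |
| 31 | 13 | 86.0% |
| 32 | 13 | 89.2% |
| 33 | 13 | 91.9% |
| 34 | 14 | 88.5% |

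**The case against.** A reader might infer that the mismatch in denominators is what destroys most of the stated power. The documents do not support that. About 22 of the points below 80% (80 − 57.5 = 22.5) are lost with all 28 analysed, through the cut-off alone. The denominator effect taken by itself, at cut-off 12, leaves 45% even at 80% confirmation, which is more than half of 80%. Power drops below 40% only when cut-off 14 meets three or more unconfirmed and unreplaced patients (34.5% at N = 25).

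A reader might also infer that the number analysed must fall below 28. It need not. Protocol 10.1 and SAP 4.3 provide for replacement of unconfirmed patients, and the preamble covers the Cohort 4 numbers given below it. Because tissue is sent soon after enrolment, results could arrive in time to act on. This part of the objection stands. Against it, Section 3.1 closes Cohort 4 at 28 treated, and neither ceiling was built with replacements in it.

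Finally, SAP 6.4 opens with an allowance for exceptions, and 6.4.1 sits beneath it. The decision rule could be an intended exception, or simply loose wording that takes confirmation for granted. The first reading fits poorly: the next sentence of 6.4 names Cohort 4 and requires confirmation, and the primary objective is limited to centrally confirmed patients. The second is plausible, but it leaves the count undefined for any N other than 28. Neither reading touches the power of 14 out of 28.

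The sensitivity-set gap is minor. It matters only if 20 mg fails the lead-in, when up to 6 patients at the abandoned dose could enter. The dose limit in 6.4 may have been meant to carry over.

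**Conclusion.** The point holds in two parts.

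1. The cut-off of 14 does not match the stated design. With a complete denominator, alpha is 0.38% and power 57.5%, against 2.9% and 82.8% for a cut-off of 12. This needs no assumption beyond the plan's own 25%, 50% and one-sided 5%.
2. The Cohort 4 denominator is defined inconsistently, and the count is not tied to the number analysed. The direction and size of the effect depend on which passage governs. Without replacement, power falls as in Step 2, under an assumed 80% to 95% confirmation rate. With replacement, the denominator does not shrink, but a fixed count is still unmatched to a number that can exceed 28.

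The sample size of 28 is adequate for the stated aim. The decision rule and the population wording need correction.

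**What to change.** - Name one Cohort 4 primary population, centrally confirmed patients treated at the recommended dose, in Protocol 3.1 and 10.1 and SAP 6.4 and 6.4.1.
- State whether the replacement rule applies to Cohort 4, and reconcile it with the stop at 28 treated and the ceilings of 34 and 168.
- Replace the fixed count with the smallest count whose exact binomial tail at 25% is at most 5% for the number analysed, and tabulate it: 9 at N = 20; 10 at 21 to 23; 11 at 24 to 26; 12 at 27 to 29; 13 at 30 to 33; 14 at 34.
- Say that this test is one-sided at 5%. At 12 out of 28, the two-sided 95% Clopper-Pearson lower limit is 24.5%, just below 25%, while the 90% limit is 26.9%. The reported 95% interval and the decision can therefore differ.
- Limit the Cohort 4 sensitivity analysis on the Response Evaluable Set to the recommended dose.

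**Cost.** Wording in both documents and one small table. Without replacement no extra patients are needed, but the plan must accept power of about 67% to 84% for N = 20 to 27. With replacement, extra patients may be needed and the ceilings may have to rise.

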6.4.1.1. Sensitivity Analyses

The primary efficacy endpoints, ORR (Cohorts 1 and 2), CBR (Cohort 3) and 6-month PFS (Cohort 4), will be analyzed based on the Response Evaluable Set using the same method as that used in the primary efficacy analysis.

6.4.2. Secondary Efficacy Analyses

The secondary efficacy endpoints are CBR (Cohorts 1, 2, 4), CR rate (Cohort 3), ORR (Cohort 4), 6-month PFS rate (Cohorts 1, 2, 3), DOR (all cohorts), PFS (all cohorts) and OS (all cohorts). The description of each efficacy endpoint is provided in Table 3. Tumor assessments will be performed as per Table 1. Response assessments will be made based on RECIST 1.1. The evaluation of endpoints will be based on central independent radiology review and the investigator or local radiologist.

CBR, CR rate and ORR will be calculated based on the best overall response. The exact 2-sided 95% CI based on Clopper-Pearson methodology will be derived for CBR, CR rate, ORR and 6-month PFS rate.

DOR, PFS, and OS will be analyzed using Kaplan–Meier product-limit estimates for each cohort. Median DOR, PFS and OS will be presented with 2-sided 95% CI if estimable. Censoring rules for PFS and OS (Table 6, Table 7) are based on the Food and Drug Administration Guidance for Industry Clinical Trial Endpoints for the Approval of Cancer Drugs and Biologics (2007). The cumulative PFS and OS will be plotted over time by cohort.

DOR will only be evaluated in patients with objective response of CR or PR. Patients who are alive and progression-free as of the data cut-off date will be censored at their last evaluable tumor response assessment prior to initiation of any new anticancer treatment. Patients who start subsequent anticancer therapy without a prior reported progression will be censored at the last tumor assessments prior to initiation of the subsequent anticancer therapy. The censoring rule for DOR is in Table 8.

Table 6. Censoring Rules for Progression-Free Survival (PFS)

No.	Situation	End Date	Outcome
1	Documented PD between scheduled visits	Date of the first assessment that determined PD	PFS event
2	Death during the study with no prior PD	Date of death	PFS event
3	Patients still on treatment without PD as of data cut-off ^a	Date of the last tumor assessment b	Censored
4	Treatment discontinuation for reasons other than PD or death, and no post baseline tumor assessments	Date of the first dose	Censored
5	Treatment discontinuation for reasons other than PD or death with post baseline tumor assessments	Date of the last tumor assessment	Censored
6	New anticancer treatment started	Date of the last tumor assessment before start of new treatment	Censored
7	Death or PD after two or more missed tumor assessments ^c	Date of the last tumor assessment before missed assessments	Censored

ĺ	8	No baseline or unreadable baseline assessment	Date of the first dose	Censored
		but readable post baseline assessments		

- a. For PFS analysis, the date of last tumor assessment refers to the date of last adequate tumor assessment.
- b. This refers to patients who were still receiving study treatment at time of data cutoff.
- c. Two or more missed tumor assessments is defined as having either one of the following two durations being longer than 4 cycles:
 - Duration between two consecutive tumor assessments
 - Duration between the last tumor assessment and death or PD

Table 7. Censoring Rules for Overall Survival (OS)

Situation	End Date	Outcome
Death before cut-off	Date of death	Death
Death after data cut-off	Date of data cut-off	Censored event
Patient still alive at data cut-off	Date of data cut-off	Censored event
Patient discontinued treatment due to any reason before data cut-off	Date last known to be alive	Censored event

Table 8. Censoring Rules for Duration of Response (DOR)

No.	Situation	End Date	Outcome
1	Documented PD between scheduled visits	Date of the first assessment that determined PD	DOR event
2	Death during the study with no prior PD	Date of death	DOR event
3	Patients still on treatment without PD as of data cut-off ^a	Date of the last tumor assessment b	Censored
4	Treatment discontinuation for reasons other than PD or death	Date of the last tumor assessment	Censored
5	New anticancer treatment started	Date of the last tumor assessment before start of new treatment	Censored
6	Death or PD after two or more missed tumor assessments ^c	Date of the last tumor assessment before missed assessments	Censored

- a. For DOR, the date of last tumor assessment refers to the date of last adequate tumor assessment.
- b. This refers to patients who were still receiving study treatment at time of data cutoff.
- c. Two or more missed tumor assessments is defined as having either one of the following two durations being longer than 4 cycles:
 - Duration between two consecutive tumor assessments
 - Duration between the last tumor assessment and death or PD

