ECOG performance status	X	X					X	X	X		See Appendix A.
12-Lead Electrocardiogram	X	X					X	X	X		At screening and 2 hours (±15 minutes) after dosing on D1 of each cycle.
Hematology	X	X		X	X	X	X	X	X		Within 24 hours prior to treatment.
Coagulation	X	X					X	X	X		Within 24 hours prior to treatment at each timepoint, and as clinically indicated.
Chemistry (Serum or plasma)	Х	X	(X)	X	X	X	X	Х	Х		Within 24 hours prior to treatment, on D1 of each cycle and on D8, D15, and D22 of Cycle 1 only. Additional collection to verify phosphorus levels on C1D4 (±24 hours). More frequent assessments may be performed if clinically indicated.
Pregnancy test	X	X					X	X	X		Serum pregnancy test required for women of child-bearing potential (WOCBP) at screening and end of treatment; serum or urine pregnancy test required at all other timepoints.
Tumor Assessments/Scans	X						see notes	X		(X)	At screening and at the end of every 8 weeks/2 cycles (± 1 week). Note that patients who discontinue without PD should continue to undergo tumor assessments/scans according to this schedule until PD is documented, new anticancer therapy is initiated, the study is terminated, or consent is withdrawn. Note that scans obtained prior to completion of the ICF may be used as the screening tumor scan if completed within 28 days of first dose.

TAS-120 Protocol TAS-120-201, Amendment 1 (Version 2.0)

	Screening Period	Treatment Period (1 cycle = 28 days)					ys)		fety ow-up	riod	Notes
	(Within 28 Days			Cycle	1		Cycles ≥2	f Tx lays)	f Tx lays) days Last		
	Prior to First Dose)	1	4 (±1d)	Day 8 (±1d)	15 (±1d)	22 (±1d)	Day 1 (±3d)	End of Tx (+0-7 days)	30 (±3) days After Last Dose	Follow-up Period	
ctDNA blood samples		X					see notes	X		(X)	Collected prior to the first TAS-120 administration on C1D1, on D1 of each alternative uneven cycle (Cycle 3, 5, 7 and ongoing), at time of PD, and at the EOT visit.
Prior & concomitant medications, AE assessments	X						\rightarrow	Х	X	X	Collect from the time ICF is signed through 30 days after administration of the last dose of study therapy or until the start of new anticancer therapy. Thereafter, only SAEs considered related to study therapy will be collected.
Survival status and subsequent therapy										Х	After discontinuation of treatment, survival follow-up should occur every 12 weeks (±2 weeks) until survival events (deaths) have been reported for 75% of enrolled patients or the study is terminated earlier by the Sponsor.

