4. STUDY DESCRIPTION

4.1. Summary of Study Design

This is a Phase 2, open-label, non-randomized, multicenter study designed to evaluate the efficacy and safety of TAS-120 and TAS-120 + fulvestrant in adult patients with locally advanced/metastatic breast cancer harboring FGFR gene amplifications. Up to approximately 168 patients will be enrolled in this study, which will be conducted at approximately 75 sites globally.

Patients will be enrolled to 1 of 4 treatment cohorts based on diagnosis and *FGFR* gene amplification status, and will receive either single agent TAS-120 in Cohorts 1-3 or TAS-120 plus fulvestrant in Cohort 4 (Figure 1).

^{*} Total number of enrolled patients including patients enrolled in Stage 1.

Figure 1. Study design flow chart

In all cohorts, a treatment cycle is defined as 28 days. All patients will receive PO TAS-120 at a dose of 20 mg QD (continuous daily dosing). Patients in Cohort 4 only will also receive intramuscular (IM) fulvestrant 500 mg on Days 1 and 15 of Cycle 1 and Day 1 of every subsequent cycle. Pre/peri-menopausal patients in Cohort 4 are required to also have ovarian suppression with goserelin as part of standard of care, having started a gonadotropin-releasing hormone (GnRH) analogue at least 4 weeks prior to the first dose of fulvestrant.

Treatment will continue until disease progression, unacceptable toxicity, or any other of the criteria for treatment discontinuation is met. For patients who discontinue treatment for reasons other than disease progression, tumor assessments should be continued until radiologic disease progression is documented or until initiation of subsequent new anticancer therapy (whichever occurs first). Patients will be followed for survival every 12 weeks (±2 weeks) until survival events (deaths) have been reported for 75% of enrolled patients or the study is terminated early by the Sponsor.

^{**} In the safety lead-in period of Cohort 4, 6 patients will initially be treated at a TAS-120 dose of 20 mg QD, with the possibility of 6 additional patients treated at 16 mg QD if 20 mg QD is not tolerated. After the safety lead-in, additional patients will be enrolled to ensure a total of 28 patients are treated at the recommended dose (including patients treated at the recommended dose in the safety lead-in.

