Chemistry (Serum or plasma)	X	X	(X)	X	X	X	X	X	Х		Within 24 hours prior to treatment, on D1 of each cycle and on D8, D15, and D22 of Cycle 1 only. Additional collection to verify phosphorus levels on C1D4 (±24 hours). More frequent assessments may be performed if clinically indicated.
Pregnancy test	X	X					X	X	Х		Serum pregnancy test required for women of child-bearing potential (WOCBP) at screening and end of treatment; serum or urine pregnancy test required at all other timepoints.
Tumor Assessments/Scans	X						see notes	Х		(X)	At screening and at the end of every 8 weeks/2 cycles (± 1 week). Note that patients who discontinue without PD should continue to undergo tumor assessments/scans every 12 weeks ±7 days until PD is documented, new anticancer therapy is initiated, the study is terminated, or consent is withdrawn. Note that scans obtained prior to completion of the ICF may be used as the screening tumor scan if completed within 28 days of first dose.

	Screening Period		Treatme	ent Perio	d (1 cycl	le = 28 da	ys)		fety ow-up	iod	Notes
	(Within 28 Days			Cycle	1		Cycles ≥2	f Tx lays)	days Last se	Follow-up Period	
	Prior to First Dose)	1	4 (±1d)	Day 8 (±1d)	15 (±1d)	22 (±1d)	Day 1 (±3d)	End of Tx (+0-7 days)	30 (±3) days After Last Dose	Follow	
ctDNA blood samples		X					see notes	X		(X)	Collected prior to the first TAS-120 administration on C1D1, on D1 of each alternative uneven cycle (Cycle 3, 5, 7 and ongoing), at time of PD, and at the EOT visit.
Prior & concomitant medications, AE assessments	Х						\rightarrow	X	X	X	Collect from the time ICF is signed through 30 days after administration of the last dose of study therapy or until the start of new anticancer therapy. Thereafter, only SAEs considered related to study therapy will be collected.
Survival status and subsequent therapy										X	After discontinuation of treatment, survival follow-up should occur every 12 weeks (±2 weeks) until survival events (deaths) have been reported for 75% of enrolled patients or the study is terminated earlier by the Sponsor.
OPTIONAL: fresh tumor biopsy for pharmacodynamic assessment	X						see notes	(X)		(X)	Baseline and at the end of Cycle 1 (C1 D28 ± 7 days). It is strongly recommended to also obtain a fresh tumor sample at the time of disease progression.

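### SAP Tables 6 and 8: the 16-week cut for two missed scans can be reached by one missed 8-weekly scan, so a documented progression or death may be censored

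*SAP*

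**What the plan says.** SAP 6.4.2, Table 6 row 7 (PFS) and Table 8 row 6 (DOR) cover the same situation: "Death or PD after two or more missed tumor assessments". The outcome is censored, with end date "Date of the last tumor assessment before missed assessments". Footnote c to both tables supplies the definition: "Two or more missed tumor assessments is defined as having either one of the following two durations being longer than 4 cycles". The first duration is the time between two consecutive scans. The second is the time from the last scan to the death or progression.

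The inputs that give this a length in days are elsewhere:

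- SAP 4.1: "In all cohorts, a treatment cycle is defined as 28 days".
- Protocol Table 1, repeated in SAP Table 1, on scans: "At screening and at the end of every 8 weeks/2 cycles (± 1 week").
- SAP Table 1: a scan taken before consent "may be used as the screening tumor scan if completed within 28 days of first dose".
- SAP Table 1, for patients who stop treatment without progression: "continue to undergo tumor assessments/scans every 12 weeks ±7 days until PD is documented". Protocol 3.2.5 also says 12 weeks, but Protocol Table 1 keeps these patients on the 8-weekly schedule.

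Protocol 10.5.2 lists the PFS censoring rules and has none for missed scans. A patient who dies without reported progression has an event on the date of death, and Table 6 row 2 says the same. SAP section 7 declares no change from the planned analyses.

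**The concern.** The rule is labelled as a test for two missed scans but is applied as a test of elapsed time. If the time limit can be passed after one missed scan, the analysis does something other than its label says. A radiologically documented progression, or a death, is then replaced by a censored time at an earlier scan. Whether that happens depends on a few days of appointment scheduling that the protocol itself permits.

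The wording also leaves a choice to the programmer. The first duration in footnote c is not tied to the event. Read literally, a long gap early in follow-up, followed by clean scans, could still censor a much later progression back to the scan before that gap. Two programmers could follow the SAP faithfully and produce different PFS and DOR curves. Both endpoints are secondary in all four cohorts.

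**Working it through.** **1. The plan's own figure.** 4 cycles × 28 days = 112 days = 16 weeks. Two scan intervals are 2 × 56 = 112 days. The cut is therefore exactly two nominal intervals, with nothing added for the visit windows.

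**2. Gap lengths with the windows.** With k scans missed between two attended scans, and each attended scan free to move ±7 days, the gap is 56(k + 1) ± 14 days.

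| Missed scans | Nominal gap | Range |
|---|---|---|
| 0 | 56 days | 42-70 days |
| 1 | 112 days | 98-126 days |
| 2 | 168 days | 154-182 days |

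A cut at 112 days lies in the middle of the one-miss range. Any cut from 126 days up to just below 154 would separate one miss from two.

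**3. Share of single misses caught.** The gap exceeds 112 days whenever the later scan's offset is greater than the earlier scan's. Assume both offsets are independent and uniform on the 15 days from -7 to +7. Of 15 × 15 = 225 pairs, 15 are ties, and (225 - 15)/2 = 105 give a longer gap: 105/225 = 46.7%. Tighter scheduling changes this little: 45.5% for ±5 days, 42.9% for ±3 and 33.3% for ±1.

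**4. The death limb.** After a scan exactly on schedule, the window for the second following scan closes at 112 + 7 = 119 days. A death on days 113-119 is treated as following two missed scans although the second is not yet overdue. If the last scan was a week early, this extends to 126 days.

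**5. Baseline scan.** Baseline may be up to 28 days before first dose. Missing only the week-8 scan then gives a gap to week 16 of 112 - 7 = 105 to 112 + 7 + 28 = 147 days (15-21 weeks). Counted from first dose, the same gap is 105-119 days.

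**6. Illustrative size.** The documents give no missed-scan rate, so this is a scenario. Assumptions: exponential PFS with median 6 months, progressions only, scans missed independently at random, scan days uniform over ±7 days, clock starting at first dose. The comparator for the Kaplan-Meier rate is no missed-scan censoring.

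| Scans missed | Reading of footnote c | Progressions censored | Change in 6-month KM rate |
|---|---|---|---|
| 5% | gap just before event | 4.7% | about +0.6 points |
| 10% | gap just before event | 9.5% | about +1.0 points |
| 5% | any earlier gap | 11.6% | 0.535 to 0.527 (-0.8) |
| 10% | any earlier gap | 21.6% | 0.542 to 0.522 (-2.0) |

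Across these settings, roughly 75-89% of the censored progressions belong to patients who never missed two scans in a row. With a cut above 126 days and the clock at first dose, none do, and total censoring falls to about 0.6-4.5%.

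A second scenario used the gap-just-before reading, with 15% of events as deaths, true 6-month PFS of 25% or 50%, and 5-20% of scans missed. The 112-day cut censored 3.5-17.4% of events and a 126-day cut 0.4-7.4%. The 6-month Kaplan-Meier rate was about 0.3-1.9 points higher with the 112-day cut.

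**The case against.** The strongest reply is that the rule is prespecified, touches only secondary endpoints that the protocol summarises descriptively, and moves the 6-month rate by a point or two. In a 28-patient cohort the exact 95% interval at 14/28 runs from 30.6% to 69.4%, so such a shift is small. The missed-scan rates are assumed. All of this stands. It limits the importance of the point but does not make the definition correct.

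Four stronger inferences are tempting, and the documents do not support them.

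- *Every single miss is censored.* It is not. An on-schedule single miss gives exactly 112 days, which is not longer than 4 cycles.
- *The rule biases PFS upward.* This is not established. In the scenario above the 6-month rate rises when only the gap before the event counts and falls when any gap counts. Patients who miss scans may be doing worse, but the documents give no evidence on that and it was not modelled.
- *Cohort 4's primary result is inflated.* SAP 6.4.1 tests it as a count, at least 14 of 28 patients observed alive and progression-free at 6 months. A patient censored early has not been observed progression-free at that time. The SAP does not say how such a patient is counted, but no inflation follows.
- *Off-treatment patients are always caught.* On a 12-weekly schedule one miss gives 2 × 84 ± 14 = 154-182 days, always above 112. These patients largely fall under Table 6 row 5 and Table 8 row 4 already, and the 12-week interval is itself contradicted by Protocol Table 1.

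The reply also has force against a bare 126-day cut. If the clock starts at a baseline scan up to 28 days before dosing, a single miss can still exceed it. With baseline uniform over 0-28 days before first dose, single misses would make up 57% (5% missed) or 38% (10% missed) of the events still censored. A baseline rule is needed.

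**Conclusion.** The defect is real and follows from the documents' own schedule: 112 days does not separate one missed 8-weekly scan from two once the ±1-week windows are applied. One missed scan with net lateness of 1 to 14 days is enough to censor a documented progression or death in the PFS and DOR analyses. The footnote also fails to say that the gap must come immediately before the event.

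The gap ranges need no assumption. The 46.7% assumes uniform scan days. The share of progressions censored, about 4.5-9.5% or about 12-22% by reading, and the 1-to-2-point shift in the 6-month rate rest on 5-10% of scans missed at random and a 6-month median. The effect is confined to the Kaplan-Meier analyses of PFS and DOR, and no decision rule is shown to change. The definition should be corrected, but the point does not threaten the design.

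**What to change.** In footnote c of Tables 6 and 8, replace the definition with one sentence: the rule applies when more than 18 weeks (126 days, being two 8-week intervals plus both 1-week windows) separate the progression or death from the last adequate assessment immediately before it, counted from first dose when baseline is the only prior assessment.

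Two related items should be settled in the same revision:

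- Reconcile the scan interval after treatment discontinuation across Protocol Table 1, Protocol 3.2.5 and SAP Table 1. If an interval other than 8 weeks applies to any patient still subject to this rule, build the limit the same way from that interval and its windows.
- Declare Table 6 row 7 in SAP section 7 as a change from Protocol 10.5.2, which has no missed-scan censoring and counts a death without reported progression as an event.

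The cost is one sentence in two footnotes and a short entry in section 7. No new data are needed. It is best done before data cut-off, so that the choice of limit cannot look data-driven.
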